Objectives	
Primary Objective: To assess the accuracy and usefulness of the Wells DVT, Wells PE and Geneva clinical decision rules in patients with a clinically suspected recurrent VTE.
 
Secondary Objectives:
 
• To assess the utility of recalibrating the existing clinical decision rules.• To derive a new CDR, specific to patients with a suspected recurrent VTE, and to assess whether this CDR would improve risk stratification as compared with existing CDRs.• To assess the accuracy of D-dimer testing in patients with suspected recurrent VTE both on and off anticoagulation.• To evaluate the accuracy of current CDRs in patients on anticoagulant therapy at the time of suspected recurrent VTE.
Duration	All consecutive eligible patients will be approached for enrolment into this study over 3 years.
Design	This is a multicentre, observational cohort study to prospectively identify potential predictors of recurrent VTE. The predictive value of individual and combined candidate predictors will be evaluated in patients with suspected recurrent VTE. All suspected recurrences will be blindly and independently adjudicated.
Significance	If the newly developed clinical decision rule is proven to accurately determine the pre-test probability in patients with a suspected acute recurrent VTE, it could be integrated in diagnostic strategies that might lower cost, avoid radiation exposure and potentially decrease over-diagnosis of patients with suspected recurrent VTE.

Target Sample Size A total of 745 participants will be enrolled at Canadian sites.

Participant Population

Inclusion Criteria

1. Outpatient with clinically suspected acute recurrent DVT or PE regardless of whether the previous event was a DVT or PE
2. Age ≥ 18 years old
3. Willing and able to give informed consent

Exclusion Criteria

1. Life expectancy less than 3 months
2. Suspicion of upper extremity thrombosis or thrombosis at an unusual site (e.g. cerebral or abdominal venous thrombosis)
3. Previous VTE was distal DVT or subsegmental PE
4. Suspected recurrent VTE is asymptomatic
5. Previously enrolled in this study

2. BACKGROUND AND RATIONALE

2.1 Background Information

The diagnostic management of suspected recurrent venous thromboembolism is challenging, since missing the diagnosis exposes the patient to the risk of (potentially) fatal PE while a false-positive diagnosis leads to unnecessary lifelong anticoagulant treatment and exposes patients to (potentially) fatal bleeding. Furthermore, not treating or a delay in treatment of recurrent DVT could worsen the symptoms of the post-thrombotic syndrome (PTS)^{17,18}.

A suspected acute recurrent VTE is common: among all patients with a suspected VTE, 20% have a history of previous VTE. In the 18 months after the withdrawal of anticoagulant therapy, 40% of patients will present with suspected recurrent VTE. The mainstays of VTE diagnosis include clinical probability, diagnostic imaging, and D-dimer testing. However, there are important implications for diagnostic management when a patient has a history of prior thrombosis. Few research studies have focused specifically on patients with suspected recurrent VTE and no study has focused on the clinical predictors of VTE in patients with suspected VTE and a history of VTE.

Clinical probability assessment is a crucial step in the management of patients with clinically suspected VTE. Pretest probability refers to the probability of a target disease or disorder being present before a diagnostic test result is known. Current diagnostic strategies for VTE rely on the sequential use of diagnostic tests based on the pretest probability of disease. Clinical decision rules (CDR) estimate the probability of a clinical outcome using simple available clinical data. Several predictive factors and CDR have been established to estimate the pretest probability of VTE.¹⁻⁵ The most commonly used CDR for suspected DVT is the Wells rule, and for suspected PE the Wells and Geneva rules. The pretest probability can aid in the interpretation of imaging test results, and to identify a group of patients at low risk of disease in whom a less intensive diagnostic work up is warranted. For example, VTE can be safely excluded in a patient deemed to be at low risk according to the CDR in combination with a negative D-dimer test result.^{6,7}

Diagnostic Imaging

Post-hoc analyses of diagnostic studies have been reassuring in terms of the safety of ruling out VTE on the basis of a non-high pretest probability using the Wells or Geneva rule in combination with a negative D-dimer in patients with a previous history of VTE.^{4,9} However, the proportion of patients in whom the diagnosis could be ruled out non-invasively was very low: approximately 10%, as compared with 30% among all-comers with suspected VTE.¹⁰

Moreover, residual thrombosis is often present after a VTE event (up to 50% of patients at one year). Therefore, it is more likely to misdiagnose a recurrent VTE in saying it is present, while it's absent. As a result of over diagnosis, these patients have a long period of exposure to anticoagulants and the associated risk of major bleeding.

Patients with a high risk according to the CDR and/or a positive D-dimer test result require imaging. However, diagnostic imaging of a suspected recurrent VTE is more challenging to interpret if a residual thrombus is present, and distinguishing a recurrent acute thrombosis from a residual thrombosis is often difficult on imaging. In a study in which all patients with a first unprovoked VTE underwent baseline imaging before discontinuing anticoagulant therapy, almost one half of patients had a suspected VTE during the first 18 months of follow-up. In 20% of patients with suspected recurrent VTE, the imaging test was positive for VTE but unchanged as compared with baseline, which means that without the results of baseline imaging tests, up to 20% of patients could have received a false-positive diagnosis of recurrent VTE.¹¹ In another study by Tan et al., 32% of patients with a suspected acute ipsilateral recurrent DVT had an inconclusive ultrasound result, yet all patients were treated with anticoagulants.¹³ In patients with no baseline imaging available,^{12,13} this may result in misdiagnoses in patients with previous VTE, with consequent unnecessary anticoagulant therapy conveying a risk of major bleeding in those over-diagnosed or potentially fatal recurrent PE in untreated patients with a true recurrence. Therefore improved risk stratification of suspected recurrent events before imaging could be of high clinical value to increase the yield of CDR and D-dimer, and thus decrease the need for imaging in this subgroup of patients. Potential benefits include reduction in radiation exposure, misdiagnosis, and costs associated with imaging, drug treatment, monitoring and medical follow-up.

2.2. Available Knowledge of Risk Stratification before Imaging

What follow are a review of the literature on predictors of recurrent VTE and the results of a retrospective study that we've performed to look at the predictive value of individual potential clinical predictors.

Clinical Probability Assessment

The Wells rule is the most well validated CDR for DVT (Refer to **Appendix A: Current Clinical Decision Rule for Suspected DVT**). In the 'original' Wells rule the item of 'deep vein thrombosis in the past' was not included²¹ but this item was added to a subsequent version of the rule, adding one point to the rule if it is present.⁷ Hence, by design, the Wells rule will have a lower specificity (less likely to be low pre-test) in patients with prior VTE. Furthermore, because the symptoms: increase in calf diameter, swelling of the leg and pain on the deep vein tract, are also symptoms of PTS and are often present in patients with a history of DVT, the performance of these variables in patients with a suspected recurrent DVT might be altered.

In patients with clinically suspected recurrent PE, the challenges for accurate diagnosis are similar to patients with suspected recurrent DVT. Patients often have persistent complaints of dyspnea after a PE.²² In patients with suspected PE the Wells rule and Geneva rule are the most validated rules (Refer to **Appendix B: Current Clinical Decision Rules for Suspected PE**).²⁻⁵ Both rules include an item related to a history of VTE in the past. Similarly to DVT, patients with a previous VTE are less likely to be classified as having a low clinical probability of PE: 26%, versus 58% in patients with no previous VTE in a post-hoc analysis of a PE diagnostic study using the Geneva score.⁴ Of note, existing CDR use 'previous VTE'

as a single criterion, regardless of the location, characteristics and time elapsed since the previous episode, although these criteria could have an important impact on the pretest probability.

D-dimer Testing

In patients with a suspected VTE event, D-dimer testing, in combination with a CDR, can safely rule out a VTE.^{7;23} In a study in 300 patients with clinically suspected recurrent DVT by Rathbun et al., 45% of the 300 patients had a negative D-dimer test and these patients were not treated with anticoagulants on the basis of this test alone.²⁰ One patient who had recurrent DVT excluded by a negative D-dimer test had confirmed VTE during 3 months follow-up (0.75% (95% CI, 0.02-4.09%). The Wells score in combination with a D-dimer test has been used to manage patients with clinically suspected acute recurrent DVT in a study by Anderson et al.¹⁹ In this study, 16 of 105 patients (15%) had an unlikely clinical probability and a normal D-dimer test; during three months follow-up none of these patients had a recurrent DVT. This study suggests that an unlikely clinical probability in combination with a normal D-dimer test result could potentially be used to exclude a DVT, but this strategy should be evaluated in a larger cohort of patients. The proportion of confirmed recurrent DVT was 22%. In a third study, among 308 patients with suspected acute PE with a VTE in the past, the D-dimer test was negative in 49 patients (16%), and none of them had a recurrent VTE during the 3-month follow-up: failure rate 0% (95% CI, 0.0-7.9%). The proportion of confirmed recurrent PE was 40%.⁴

In conclusion, D-dimer testing may play a role in excluding a recurrent VTE; however the presently available studies show broad confidence intervals for the 3 month recurrent VTE failure rates after a negative test result. Most importantly, the combination of current CDRs and D-dimer testing shows a low proportion (10-16%) of patients who could have VTE excluded by a low pretest probability and a negative D-dimer test result.

2.2.2. A survey of thrombosis experts

As a second approach to identify candidate predictors, we performed a survey in our own nation-wide collaborative research group to evaluate what the thrombosis experts consider potential predictors of recurrent VTE, based on their clinical experience in managing these patients. The following items were proposed by thrombosis experts as potential clinical predictors and will be collected in this study:

Pulmonary embolism

- Leg symptoms and signs of DVT
- Tachycardia
- Cancer
- Recent surgery or immobilization
- Subtherapeutic INR or recent dose reduction
- Clean X-ray
- No alternative diagnosis

Deep vein thrombosis of the leg

- Tenderness in deep vein distribution

- New onset of significant leg swelling
- New onset of edema or worsening of chronic state of lower extremity edema
- Cancer
- Subtherapeutic INR or recent dose reduction
- Recent surgical procedure
- No alternative diagnosis

General predictors for DVT and PE

- Age
- Gender
- Whether previous event was provoked/unprovoked
- Active cancer
- D-dimer testing at moment of suspected recurrence and on baseline visit
- Recent (within one year) discontinuation of anticoagulation after previous event
- Estrogen therapy

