9.5 Primary Outcome Analysis

The primary analysis is the validation of existing CDRs. The Wells DVT score will be computed in all participants with suspected DVT, and both the Wells' PE score and revised Geneva score will be computed in participants with suspected PE. Calibration will be assessed by comparing predicted and observed rates of confirmed VTE (Hosmer-Lemeshow 'goodness-of-fit test'), and discrimination will be assessed using the area under the receiver operating characteristics curve (c-statistic). Further, the proportion of participants with the combination of a non-high clinical probability and negative D-dimer test, and the false-negative rate of this combination (ie the proportion of participants with confirmed recurrent VTE among those with a non-high clinical probability and negative D-dimer) will be estimated along with their 95% confidence intervals.

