9.6 Secondary Outcome Analysis

9.5.1 Recalibration / minor adjustment to existing rules

Recalibration

For each existing CDR, a multivariate regression analysis including all predictors from the CDR will be conducted. The regression coefficients obtained from this model in our sample will be examined to evaluate whether changes in the points given to each predictor in the rule need to be modified in patients with a suspected recurrent VTE.

Minor adjustments

For each existing CDR, a multivariate regression analysis including all predictors from the CDR will be performed. Candidate predictors will also be included in the analysis, but keeping in the model predictors from the CDR. Should one or two candidate predictors significantly improve risk stratification, a modified score could be proposed for patients with suspected recurrent VTE. Potential improvements in classification will be assessed using the Net Reclassification Improvement and the Integrated Discrimination Improvement indices.

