9.5.2 Derivation of a new CDR

Univariate Analysis

Univariate analysis will be used to assess the association between each variable and VTE recurrence. This process will aid selection of the best variables for the multivariate analysis. The appropriate univariate technique will be chosen according to the type of data.

Multivariate Analysis

Multivariate analysis will derive one model to predict recurrent VTE. Those variables found to be strongly associated with the outcome measure ($P<0.05$), by the univariate analysis and have good inter-observer reliability ($\kappa >0.6$), will be combined using logistic regression. For continuous and ordinal variables various cut-points will be examined to determine the optimal cut-point(s). The derived CDR must be easy to use by clinicians and therefore should contain as few variables as possible. Thus, only the most informative variables will be kept in the final model. Points for the score will be attributed according to regression coefficients. The CDR will be presented in clear narrative form that does not require computation or use of statistical aids. Discrimination and calibration of the new CDR will be estimated and compared to those obtained with existed/modified CDRs using the same indices as described above.

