9.5.3 D-dimer testing

We will estimate what the proportion of participants will be with a non-high pre-test probability (using all the possible stratification tools described above) and negative D-dimer test result and in whom imaging could potentially be withheld. We furthermore will estimate what the false negative rate will be in this proportion of participants. These proportions will be computed along with their 95% confidence intervals.

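### Sections 9.5.1 and 9.5.2 leave presentation D-dimer eligible as an item of the modified or new rule; if selected, the c-statistic, NRI and IDI gain over Wells and Geneva mixes D-dimer's information with that of the clinical items

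*Combined protocol and SAP*

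**What the plan says.** Section 2.2.2 presents its expert survey "As a second approach to identify candidate predictors". Among the general predictors for DVT and PE it lists "D-dimer testing at moment of suspected recurrence and on baseline visit". Appendix D, which section 6.2.1 treats as the full predictor list, has D-dimer under laboratory tests. Section 6.2.2 has it measured in every participant with one central assay.

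Section 9.5.1 (minor adjustments) states: "Candidate predictors will also be included in the analysis, but keeping in the model predictors from the CDR". Any improvement is "assessed using the Net Reclassification Improvement and the Integrated Discrimination Improvement indices". Section 9.5.2 states: "Univariate analysis will be used to assess the association between each variable and VTE recurrence". Variables with univariate P<0.05 and kappa above 0.6 then enter a logistic model, whose discrimination and calibration are "compared to those obtained with existed/modified CDRs using the same indices as described above". Neither section names a variable that may not enter.

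Other places treat D-dimer as a separate step. Section 2.1 defines pretest probability as existing before a test result is known, and speaks of the joint yield of rule and D-dimer. Section 9.5 estimates "the proportion of participants with the combination of a non-high clinical probability and negative D-dimer test". Section 9.5.3 does the same for a "non-high pre-test probability (using all the possible stratification tools described above) and negative D-dimer test result".

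**The concern.** The secondary objective in section 1.2 asks whether a new rule stratifies risk better than the existing ones. Wells DVT, Wells PE and revised Geneva (Appendices A and B) contain no D-dimer item. If the modified or new rule contains one, its advantage on c-statistic, NRI and IDI has two sources that the planned comparison cannot separate: better clinical items, and a laboratory test that the existing pathway applies anyway as the next step. A reader could credit the clinical items with a gain that D-dimer supplied.

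Selection is plausible. Section 2.2.3 reports p<0.01 for a positive D-dimer at presentation in the team's own retrospective cohort. Section 9.5.1 has no kappa filter. The kappa filter in 9.5.2 has no clear meaning for a single central assay, so it cannot be relied on to keep D-dimer out.

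**Working it through.** **Plan's own figure.** The documents give no figure for this comparison. The sample size reproduces: 100/0.29 = 345 (rounded up) and 100/0.25 = 400, total 745. The point does not change it.

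**D-dimer inputs (section 2.2, D-dimer Testing).**
- PE: 308 patients, 40% confirmed, so 123 with PE and 185 without; 49 negative tests, no misses. Sensitivity (se) is 1.000 and specificity (sp) is 49/185 = 0.265. As a pessimistic case, take 4 misses (4/49 = 8.2%, slightly beyond the quoted upper limit of 7.9%): se = 119/123 = 0.967, sp = 45/185 = 0.243.
- DVT: 300 patients, 1 miss, failure rate 0.75%, so 134 negatives (1/134 = 0.75%). Prevalence is not given for that study. I assume 22% (66 events, 234 non-events) to 29% (87 and 213), figures the protocol gives for other cohorts. Then se = 65/66 = 0.985 and sp = 133/234 = 0.568, or se = 86/87 = 0.989 and sp = 133/213 = 0.624. At the upper limit, 0.0409 × 134 = 5.5 misses: se = 60.5/66 = 0.917 and sp = 128.5/234 = 0.549, or se = 81.5/87 = 0.937 and sp = 128.5/213 = 0.603.

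**Assumptions not in the documents.** The existing clinical rule has c = 0.65, the new clinical items alone give c = 0.70, and the clinical score is normal within disease groups.

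**Formula, D-dimer independent of the score given disease status.** Let δ = √2·Φ⁻¹(c) and Λ = ln[se/(1−sp)] − ln[(1−se)/sp]. Then

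c with D-dimer = [se(1−sp) + (1−se)sp]·c + se·sp·Φ((δ²+Λ)/(√2·δ)) + (1−se)(1−sp)·Φ((δ²−Λ)/(√2·δ)).

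With no misses this reduces to sp + (1−sp)·c. For PE: 0.265 + 0.735 × 0.65 = 0.743, and 0.265 + 0.735 × 0.70 = 0.779 (unrounded sp).

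| Case | 0.65 rule + D-dimer | 0.70 rule + D-dimer | New rule with D-dimer minus unmodified 0.65 | D-dimer on both sides |
|---|---|---|---|---|
| PE, 0 misses | 0.743 | 0.779 | 0.129 | 0.037 |
| PE, 4 misses | 0.716 | 0.754 | 0.104 | 0.037 |
| DVT 22%, 1 miss | 0.842 | 0.863 | 0.213 | 0.022 |
| DVT 22%, upper limit | 0.802 | 0.825 | 0.175 | 0.023 |
| DVT 29%, 1 miss | 0.863 | 0.882 | 0.232 | 0.019 |
| DVT 29%, upper limit | 0.832 | 0.852 | 0.202 | 0.021 |

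Differences are taken before rounding. The true clinical gain is 0.05 in every row.

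**Dependence.** Independence is favourable to D-dimer, so I simulated the same cases with a latent correlation between D-dimer and score within disease groups (1,000,000 participants per case).
- PE: 0.085-0.106 at correlation 0.3 and 0.076-0.091 at 0.5. With D-dimer on both sides, about 0.04.
- DVT: 0.150-0.203 at 0.3 and 0.133-0.184 at 0.5. With D-dimer on both sides, 0.020-0.027.

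**Share due to D-dimer** (total minus the both-sides difference). Lowest PE case: 0.076 − 0.041 = 0.035, or 46%. Highest PE case: 0.129 − 0.037 = 0.092, or 71%. DVT runs from 0.133 − 0.027 = 0.106 (80%) to 0.232 − 0.019 = 0.213 (92%).

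**IDI.** Under independence, with clinical c from 0.60 to 0.75 and unchanged clinical items, adding D-dimer alone gives an IDI of about 0.08-0.11 (PE) and 0.21-0.26 (DVT).

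**The case against.** The strongest reply is that the intent is already clear. A pre-test probability precedes test results by the protocol's own definition, and 9.5.3 pairs every stratification tool with D-dimer, which presupposes rules without it. Appendix D works partly as a collection list: it includes inpatient/outpatient status, which is constant in an outpatient study, and D-dimer must be collected anyway for the primary analysis. Section 2.2.2 reports what experts proposed. All this makes a D-dimer-free rule the likelier intention. But no sentence says so, and the text that does name predictors includes D-dimer, so the plan can be followed literally either way.

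Three stronger readings are tempting and are not supported:
- **That 9.5.3 would be biased by using D-dimer twice.** The group that is non-high on the rule and D-dimer negative is still well defined, its yield and false-negative rate are valid estimates, and the existing rules are paired with D-dimer there too. The effect is redundancy: the rule's rule-out group would come close to all D-dimer-negative participants.
- **That no like-for-like comparator can arise.** Section 9.5.2 also names modified rules as comparators, and one of those might contain D-dimer. Nothing ensures that it would.
- **That D-dimer will be in the rule.** It must pass the selection steps and be retained. This is plausible, not certain.

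It is also true that a refit without D-dimer needs no new data. The plan does not call for one, so it would be a choice made at analysis, possibly after the c-statistics are seen.

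**Conclusion.** The point holds, conditionally. If presentation D-dimer is selected, the c-statistic, NRI and IDI comparison with the unmodified rules does not isolate the value of the clinical items. Under the stated assumptions, D-dimer would supply most of the apparent c-statistic gain for DVT and about half or more for PE.

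These sizes are illustrations. They rest on assumed clinical c-statistics, an assumed DVT prevalence and an assumed degree of dependence, and they do not separate participants on anticoagulants. The direction does not depend on the exact values.

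The primary validation of the existing rules is unaffected. Severity is minor to moderate, confined to the secondary analyses of modified and new rules.

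**What to change.** State in 9.5.1 and 9.5.2 that D-dimer at presentation is not eligible as an item in the modified or new pre-test rules. Earlier D-dimer values (baseline visit, or after stopping anticoagulation) may remain candidates.

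Alternatively, if a rule containing presentation D-dimer is derived, report its c-statistic, NRI and IDI against existing rule plus D-dimer, in addition to the planned comparison with the existing rules. That planned comparison should stay, because it is the one section 1.2 sets as the objective. In 9.5.3, report that rule's own rule-out group without applying D-dimer again.

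Cost: one sentence in each of 9.5.1 and 9.5.2, and one more in 9.5.3 under the alternative. No new data are needed and the sample size does not change. If D-dimer is made ineligible, the new rule's headline c-statistic will probably be lower.
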